9.3.2 Acne Patient Self-Questionnaire

Subjects will be asked to complete Acne Patient Self-Questionnaire. The questionnaire is paper-based and will be completed by subjects during clinic visits (see Appendix 2). Subject responses will be entered in the eCRF by the study site and the completed questionnaires kept as part of the subject's source document. Study site staff must review all forms to ensure complete responses prior to a subject leaving the study site.

9.4 Assessment of Safety

9.4.1 Physical Examination

A complete physical examination will be conducted at screening and Week 12 or Early Termination visits and cover general appearance, dermatological, head, ears, eyes, nose, throat, respiratory, cardiovascular, abdominal, neurological, musculoskeletal, and lymphatic body systems. Height and weight will be recorded as part of the screening physical exam and only the subject's weight will be recorded with the end of study physical exam. A symptom-directed physical exam may be performed at subsequent visits as needed. Following baseline, any new findings or findings that have worsened in severity should also be recorded as an AE.

Physical exam findings will be recorded in the eCRF.

9.4.2 Vital Signs

Vital signs, including body temperature, respiratory rate (breath per minute), pulse (beats per minute), and blood pressure (mmHg), will be obtained with the subject in the seated position, after sitting for at least 5 minutes. Any abnormal findings which are new or worsened in severity and clinically significant, in the opinion of the Investigator, will be recorded as an AE.

Vital sign measurements will be recorded in the eCRF.

9.4.3 ECGs

12-lead ECG measurements will be obtained in all subjects. The subject should rest quietly for at least 5 minutes in a supine position prior to ECG collection. The ECG should be obtained either prior to the time of blood collection, or at least 15 minutes afterwards.

At screening, the Investigator will use the machine-read ECG to determine subject eligibility. The medical monitor may be consulted if needed for interpretation of ECGs.

All study sites will be supplied with standardized, validated digital 12-lead ECG (12-lead at 25 mm/sec reporting rhythm, ventricular rate, the RR interval, the PR interval, QRS duration, QT and QTcF intervals) equipment capable of recording, storing, and printing producing high resolution 12-lead ECG data by the central laboratory. Study sites will be trained on the use of the equipment prior to study start.

Machine-read ECG recordings will be collected and analyzed centrally. Data will be transferred electronically to the database.

9.4.4 Laboratory Evaluations

Laboratory tests will be collected to evaluate safety in all study subjects and analyzed using a central laboratory. Labs will be collected per the Schedule of Visits and Procedures (see Appendix 1) or more frequently as clinically indicated. Laboratory samples are to be shipped on the same day as collected. No more than 4 mL/kg total will be collected over an 8-week period in subjects under legal adult age. Laboratory tests are described below.

Hematology: hematocrit, hemoglobin, red blood cell (RBC) count, white blood cell count and differential (%), mean corpuscular hemoglobin (MCH), mean corpuscular hemoglobin concentration (MCHC), mean corpuscular volume, platelet count, absolute neutrophils, absolute lymphocytes, absolute monocytes, absolute eosinophils, and absolute basophils. RBC morphology should be performed if indicated.

Chemistry: sodium, potassium, chloride, calcium, phosphorus, bicarbonate, uric acid, blood urea nitrogen (BUN), creatinine, total protein, albumin, aspartate aminotransferase (AST), alanine aminotransferase (ALT), alkaline phosphatase, bilirubin (total and direct), and glucose (fasting or non fasting).

Serum pregnancy testing will be performed at the screening and Week 12 (study exit) or Early Termination visits. Urine pregnancy testing (beta human chorionic gonadotropin [β -hCG]) will be performed at Baseline/Day 1, and the Weeks 4 and 8 visits for all females unless postmenopausal/sterile.

Urinalysis: pH, specific gravity, protein, glucose, ketones, bilirubin, blood, nitrite, urobilinogen, leukocyte esterase. A microscopic examination of urine will be performed if clinically indicated (e.g. a positive dipstick for protein, blood, leucocyte esterase) in the opinion of the Investigator based on the findings of the urinalysis or clinical signs and symptoms. Any new or worsened clinically significant laboratory result is to be recorded as an AE after study drug dosing.

Screening laboratory values must be reviewed by the Investigator prior to subject enrollment. Subjects will be screen failed for clinically significant laboratory values. Screening laboratory tests may be repeated one time in order to confirm out of range results clinical significance at the discretion of the investigator.

The central laboratory must be used for any laboratory testing required for a subject during study participation, including laboratory testing needed for unscheduled visits. If an immediate result is required to adequately care for a subject, a duplicate sample may be submitted to a local lab. Clinically significant laboratory results must be recorded as an AE, preferably as a diagnosis rather than individual test results. Any subject who has a clinically significant laboratory test result will be evaluated by the Investigator, and will be treated and/or followed up until the value returns to clinically acceptable level, in the opinion of the investigator.

9.4.5 Local Skin Reactions (LSRs)

All subjects will be assessed for LSRs, on the face, at each visit. LSRs include burning/stinging, pruritus, erythema, dryness and peeling. Each LSR will be scored as 0 (None), 1 (Mild), 2 (Moderate) or 3 (Severe). LSRs observed on a visit day will not be recorded as adverse events

unless scored as 3 (Severe). Local skin reactions experienced by the subject in between study visits are to be recorded as an AE.

Burning/stinging and pruritus will be assessed by the subject (Table 3) and erythema, dryness and peeling will be assessed by the Investigator/designee (Table 4). Subjects will be read the definition of each subject-assessed LSR and asked to select the appropriate definition. The corresponding score will be assigned by the site and entered in the eCRF.

Table 3: Subject Assessed Local Skin Reactions

Score	Grade	Burning/Stinging	Pruritus
0	None	No stinging/burning	No pruritus
1	Mild	Slightly warm, tingling sensation; not really bothersome	Occasional, slight itching/scratching
2	Moderate	Definite warm; tingling/stinging sensation that is somewhat bothersome	Intermittent itching/scratching which does not disturb sleep
3	Severe	Hot, tingling/stinging sensation that has caused definite discomfort	Bothersome itching/scratching which disturbs sleep

Table 4: Investigator Assessed Local Skin Reactions

Score	Grade	Erythema	Dryness	Peeling
0	None	None	None	None
1	Mild	Slight erythema: very light- pink	Perceptible dryness with no flakes or fissure formation	Mild diffuse peeling
2	Moderate	Dull red, clearly distinguishable	Easily noted dryness and flakes but no fissure formation	Moderate diffuse peeling
3	Severe	Deep/dark red	Easily noted dryness with flakes and fissure formation	Moderate to prominent, dense peeling

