9.4.6.1 Reporting

Only AEs that occur during or following study treatment with the study drug will be reported in the AE section of the eCRF. Events recorded prior to study treatment with the drug will be reported in the Medical History section of the eCRF as appropriate. All AEs occurring during the course of the study will be individually recorded in the eCRF. A condition that is present prior to administration of study drug and that worsens after administration of study drug should be reported as an AE. Information regarding the onset, duration, severity, action taken, outcome, and relationship to study drug will be recorded.

New or worsening abnormal laboratory values and/or vital signs are to be recorded as AEs if they are considered to be of clinical significance by the Investigator or meet the criteria of an SAE as described in Section 9.3.7.

Unless a diagnosis is available, signs and symptoms must be reported as individual AEs in the eCRF; a diagnosis is preferred.

The severity of an AE will be designated as mild, moderate or severe. The term "severe" is used to describe the intensity of an adverse event; the event itself, however, may be of relatively minor clinical significance (e.g. 'severe' upper respiratory infection). Severity is not the same as "serious". Seriousness of AEs is based on the outcome/action of an AE. (See Section 9.3.7.)

The relationship of the AE to the study treatment should be determined by the Investigator and will be based on the following two definitions:

Not related: An AE is defined as "not related" if the AE is not judged to be associated with the study drug and is attributable to another cause

Related: An AE is defined as "related" where a causal relationship between the event and the study drug is a reasonable possibility (possibly or probably related). A reasonable causal relationship is meant to convey that there are facts (e.g., evidence such as dechallenge/ rechallenge) or other clinical arguments to suggest a causal relationship between the AE and study treatment.

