9.4.8 Dosing Changes due to AEs

Dose interruptions are allowed should a subject experience intolerable treatment-related adverse events (e.g., pruritis) on study. In cases where the Investigator feels a dose interruption is warranted, the subject should be instructed to interrupt study drug application to allow symptoms to resolve. Subjects should be instructed to return to the twice daily application regimen within 2 days of dose interruption.

Dosing interruptions are to be recorded in the subject diary as a missed dose.

Study drug must be discontinued if an adverse event is deemed persistent and if continuation of study drug would not be in the best interest of the subject.

Refer to Section 10.3 for further information regarding discontinuation of study drug or early withdrawal

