Treatment compliance will be based on the expected number of doses given the treatment period duration. Treatment period duration will be computed from the Baseline/Day 1 visit date and the Week 12/Early Termination (ET) visit date. If a subject does not have a Week 12/ET visit, treatment period duration will be calculated based on the date of last dose or last completed visit date, whichever is later. That is, treatment period duration will be computed from the Baseline/Day 1 date and the end of treatment period date, where the end of treatment period date is given by

- If the subject completed the Week 12/ET visit, the end of treatment period date will be:
 - The date of the Week 12/ET visit if the expected number of applications on the date of last application is one;
 - The day prior to the Week 12/ET visit if the expected number of applications on the date of last application is two;
- If the subject did not complete the Week 12/ET visit, the end of treatment period date will be the date of last dose or last completed visit, whichever is later.

Then treatment period duration may be calculated as:

Treatment Period Duration = End of Treatment Period Date – Day 1 Date + 1.

If the treatment period duration exceeds 88 days, treatment period duration will be considered 88 days. In addition to treatment period duration, missed applications due to treatment-related AEs

will be considered when determining the expected number of doses for each subject. If a treatment-related AE (regardless of location) requires interruption of study drug during the treatment period, missed applications during the AE (onset date to resolution date) will be deducted from the expected number of doses. Therefore, the expected number of applications will be calculated as:

Expected Applications = 2*(Treatment Period Duration - 2)

- + Expected Applications on Date of First Application
- + Expected Applications on Date of Last Application
- Applications Missed Due to a Treatment-Related AE.

If Treatment Period Duration = 1, then

Expected Applications Expected Applications on Date of First Application

– Applications Missed Due to a Treatment-Related AE.

Percent compliance will be calculated from total number of applications and total number of expected applications as follows:

Percent Compliance = 100*(Total Applications/Expected Applications).

Percent compliance will not be calculated for subjects who are lost to follow-up.

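### The visit-day exception for local skin reactions in Protocol 9.4.5 is not reconciled with 9.4.1, 9.4.6.1 and 9.4.8, so a grade 1–2 reaction that changes dosing can go unrecorded as an adverse event

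*Protocol*

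**What the plan says.** Protocol 9.4.5 scores five facial LSRs (burning/stinging, pruritus, erythema, dryness, peeling) from 0 to 3 at each visit and splits AE recording by timing:

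- On a visit day: "LSRs observed on a visit day will not be recorded as adverse events", with grade 3 as the only exception.
- Otherwise: "Local skin reactions experienced by the subject in between study visits are to be recorded as an AE", at any grade.

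Three other protocol sections bear on the same reactions, and none mentions LSRs as an exception:

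- 9.4.1 Physical Examination: after baseline, "any new findings or findings that have worsened in severity should also be recorded as an AE". The complete examination includes the skin.
- 9.4.6.1 Reporting: "All AEs occurring during the course of the study will be individually recorded in the eCRF", and "A condition that is present prior to administration of study drug and that worsens after administration of study drug should be reported as an AE".
- 9.4.8 Dosing Changes due to AEs: "Dose interruptions are allowed should a subject experience intolerable treatment-related adverse events (e.g., pruritis) on study". No grade is given.

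The SAP attaches consequences to AE status:

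- 7.9.8.2 summarises treatment-emergent AEs and AEs leading to discontinuation.
- 7.8.4 keeps in the per-protocol (PP) set subjects who stop treatment or the study for a related AE, or for documented lack of effect.
- 7.9.8.1 provides that, for a treatment-related AE requiring interruption, "missed applications during the AE (onset date to resolution date) will be deducted from the expected number of doses".

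SAP 7.9.8.4 separately tabulates LSR scores at every grade.

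**The concern.** For a topical product, the local reactions that matter most for tolerability are those that make a subject pause, stop or need treatment. Under the literal visit-day rule, such a reaction is not an AE if it was graded 1 or 2 at the visit, whatever it led to. Other sections point the other way, and nothing says which prevails.

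The LSR score does not replace the missing record. Section 9.4.6.1 collects onset, duration, severity, action taken, outcome and relationship for AEs, whereas 9.4.5 describes only a score for LSRs. Section 9.4.8 has an interruption entered in the diary as a missed dose. Without an AE record, nothing described in the protocol links the reaction to the dosing change.

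At stake are the absolute rates of treatment-emergent AEs and of AEs leading to discontinuation. The PP and compliance provisions that depend on a related AE having been recorded are also affected.

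**Working it through.** The plan gives no figure on this point to reproduce. The check sets the rules side by side for worked cases, then sizes the compliance effect.

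**Cases under the text**

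1. *Facial erythema, grade 0 or 1 at baseline, grade 2 at the Week 12 visit.* Under 9.4.5 it is not an AE. Under 9.4.1 it is a new or worsened finding and therefore an AE. Protocol 8.7 schedules the complete examination and the LSR assessment at this same visit. If baseline was grade 1, the worsening rule in 9.4.6.1 also makes it an AE.
2. *Pruritus scored 2 at a visit.* Table 3 defines this grade as intermittent itching that leaves sleep undisturbed, and gives no recall period. The subject can answer only from the time before the visit. The visit-day rule says no AE, the between-visit rule says AE, and 9.4.5 does not choose. Grade 3 raises no such question, because it is an AE under both rules.
3. *Pruritus or burning scored 2 at a visit, and dosing interrupted because of it.* Under the visit-day rule it is not an AE. Under 9.4.8 the interruption is allowed because of an AE. If the reaction continues after the visit, the between-visit rule should capture it; if not, only the score remains.
4. *The same reaction, and the subject stops study drug.* If no AE is recorded, the event cannot appear as an AE leading to discontinuation (SAP 7.9.8.2), and the related-AE route into the PP set (SAP 7.8.4) is not met. The subject can then be excluded, for example for missing the Week 12 visit.
5. *Reaction on the trunk.* Protocol 6.5 allows application to chest, shoulders and back, but LSRs are assessed on the face only. The text does not say whether the visit-day exception reaches truncal reactions. SAP 7.9.8.2 summarises AEs by face-only versus face-plus-trunk treatment.

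**Size of the compliance effect**

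Assumption: a treatment period of 84 days (12 weeks), with two applications expected on both the first and last dates.

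- Expected applications (SAP 7.9.8.1 formula): 2 × (84 − 2) + 2 + 2 = 168.
- Section 9.4.8 has subjects return to twice-daily use within 2 days. One 2-day interruption is 2 × 2 = 4 applications, and 4/168 = 2.4%.
- Compliance if no AE is recorded: 164/168 = 97.6%. If a related AE is recorded and the doses are deducted: 164/164 = 100%.
- The PP lower limit is 80%, and 0.80 × 168 = 134.4. With 33 undeducted misses compliance is 135/168 = 80.4%; with 34 it is 134/168 = 79.8%. Crossing the limit therefore takes at least 34 misses, and 34/4 = 8.5, so nine 2-day interruptions.

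**The case against.** The best defence is that 9.4.5 names LSRs specifically and can be read as a deliberate exception to the general AE rules, a sensible way to avoid double counting in the AE and LSR tables. Its two sentences divide by timing and do not contradict each other on their face. Every visit score is entered in the eCRF and summarised under SAP 7.9.8.4, by visit and as worst grade. Reasons for discontinuation are recorded (Protocol 10.2) and summarised (SAP 7.9.3). Because 9.4.8 permits interruption for an adverse event, a site following it would arguably treat the reaction as one. Outside Week 12 or early termination, 9.4.1 makes the examination symptom-directed and as needed, which narrows the overlap.

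Most of this stands, and it limits the point in three ways.

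- A reader might infer that the protocol has three flatly contradictory rules, or that every grade 1–2 LSR can be classified either way. The documents do not support that. For an ordinary visit-day sign that changes nothing, the specific-exception reading is natural, although precedence is unstated.
- A reader might picture a long interruption that removes a subject from the PP set: 22 days off drug is 44 applications, and 124/168 = 73.8%. A reaction lasting that long is experienced between visits, so 9.4.5 already makes it an AE at any grade. If it is treatment-related, the doses are deducted.
- A reader might infer that sites will classify differently. That is possible but not shown. The rules are the same for both blinded arms, so no bias between arms is demonstrated.

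The defence does not supply an exception for a grade 1–2 visit-day reaction that changes dosing, or a rule for a reaction that spans a visit.

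**Conclusion.** The point holds in a limited form. The visit-day exception in 9.4.5 is not reconciled with 9.4.1, 9.4.6.1 or 9.4.8, and 9.4.5 does not say which of its own two rules governs a reaction present both between visits and on a visit day. Taken literally, it leaves out of the AE record a grade 1–2 visit-day reaction that leads to interruption, discontinuation or treatment.

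Such a reaction could be missing from the AE summaries, and a subject who stops because of it could lose the related-AE route into the PP set. How many subjects this would affect cannot be derived from the documents. The compliance effect is small at 2.4 percentage points per 2-day interruption, under the 84-day, 168-application assumption. The reaction itself remains visible in the LSR tables; what can be lost is its AE status and its link to the dosing change. The amendment is worth making because it is cheap and concerns the main local tolerability counts.

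**What to change.** Keep the between-visit rule as it is and amend the wording around it:

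- In 9.4.5, record a visit-day LSR as an AE if it is grade 3, or if it leads to dose interruption, study drug discontinuation or treatment.
- In 9.4.5, state that a reaction also experienced between visits follows the between-visit rule, and that the visit-day exception applies to the face only.
- In 9.4.1 and 9.4.6.1, state that other visit-day facial LSRs follow 9.4.5.

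Sending all remaining grade 1–2 reactions to the LSR form alone would be simpler but would lose data. LSRs are scored only at clinic visits and only on the face, so a mild reaction that resolves between visits, or one on the trunk, could be recorded nowhere.

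The change affects recording only and leaves patient management as it is. The cost is a protocol wording change and an update to the eCRF completion guideline. A few more reactions will appear in the AE tables.

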9.4.6 Adverse Events

An adverse event (AE) is defined as any untoward medical occurrence associated with the use of a study drug in humans, whether or not considered drug related. An AE can, therefore, be any unfavorable and unintended sign (including an abnormal laboratory finding), symptom or disease temporally associated with the use of the study drug, whether or not related to the investigational product.

AEs will be monitored throughout the study. Subjects will be instructed to inform the Investigator and/or study staff of any AEs. At each visit, subjects will be asked about AEs in a non-specific manner using open-ended questions so as not to bias the response (e.g., How have you been since the last visit?). Specific inquiry regarding reported AEs will be conducted when applicable. All AEs will be documented and recorded in the subject's eCRF.

Any subject who has an AE (serious or non-serious) or clinically significant abnormal laboratory test value will be evaluated by the Investigator, and will be treated and/or followed up until the symptoms or values return to normal or to clinically acceptable levels, as judged by the

Investigator. A physician, either at clinical site, or at a nearby hospital emergency room, will administer treatment for any serious adverse events (SAEs), if necessary. When appropriate, medical tests and examinations will be performed to document resolution of event(s).

9.4.6.1 Reporting

Only AEs that occur during or following study treatment with the study drug will be reported in the AE section of the eCRF. Events recorded prior to study treatment with the drug will be reported in the Medical History section of the eCRF as appropriate. All AEs occurring during the course of the study will be individually recorded in the eCRF. A condition that is present prior to administration of study drug and that worsens after administration of study drug should be reported as an AE. Information regarding the onset, duration, severity, action taken, outcome, and relationship to study drug will be recorded.

New or worsening abnormal laboratory values and/or vital signs are to be recorded as AEs if they are considered to be of clinical significance by the Investigator or meet the criteria of an SAE as described in Section 9.3.7.

Unless a diagnosis is available, signs and symptoms must be reported as individual AEs in the eCRF; a diagnosis is preferred.

The severity of an AE will be designated as mild, moderate or severe. The term "severe" is used to describe the intensity of an adverse event; the event itself, however, may be of relatively minor clinical significance (e.g. 'severe' upper respiratory infection). Severity is not the same as "serious". Seriousness of AEs is based on the outcome/action of an AE. (See Section 9.3.7.)

The relationship of the AE to the study treatment should be determined by the Investigator and will be based on the following two definitions:

Not related: An AE is defined as "not related" if the AE is not judged to be associated with the study drug and is attributable to another cause

Related: An AE is defined as "related" where a causal relationship between the event and the study drug is a reasonable possibility (possibly or probably related). A reasonable causal relationship is meant to convey that there are facts (e.g., evidence such as dechallenge/ rechallenge) or other clinical arguments to suggest a causal relationship between the AE and study treatment.

